PASS Information

Title	Utilisation of dulaglutide in European countries: A cross-sectional, multi-country and multi-source drug utilisation study using electronic health record databases.
Version identifier	Version 1.0
Date of last version	01 May 2016
EU PAS Register No:	Study not registered
Active substance	Dulaglutide (ATC code: A10BX)
Medicinal product(s):	Trulicity 0.75 mg solution for injection Trulicity 1.5 mg solution for injection
Product reference:	EU/1/14/956
Procedure number:	EMA/H/C/002825
Marketing authorisation holder(s)	Eli Lilly Nederland B.V.
Joint PASS	No
Research question and objectives	
The purpose of this study is to describe how dulaglutide is used among different patient groups in European countries.
 
Primary objective: To describe the frequency of dulaglutide use in the population and characterise by age, gender, main co-morbidities and main co-prescriptions overall and in the following subgroups of interest:
 
 ○ Populations of interest: 
 • Patients with severe renal failure • Patients with hepatic disease • Patients with heart failure • Patients with severe gastrointestinal disease • Children and adolescents <18 years of age • Elderly patients ≥75 years • Pregnant and breastfeeding women ○ Medication use : 
 • Medication errors • Off-label use 
Secondary objective: To describe the off-label use among each of the above populations of interest.

Country(-ies) of study	Several countries will be selected from the databases under consideration (France, Germany, Spain, Sweden and the United-Kingdom) based on the criteria described in the feasibility analysis (see Section 9.5.2).
Author	IMS Health [name], Medical director [name], Senior Medical writer and project lead

Approval Date: 07-Jun-2016 GMT

Marketing Authorisation Holder

Marketing authorisation holder (MAH)	Eli Lilly Nederland B.V.
MAH contact person	[name], Pharmacoepidemiologist Eli Lilly and Company

1. Table of Contents

Section	Page
1. Table of Contents.....	3
2. List of Abbreviations	7
3. Responsible Parties	9
4. Abstract	10
5. Amendments and Updates.....	14
6. Milestones.....	15
7. Rationale and Background	16
8. Research Question and Objectives.....	17
9. Research Methods.....	18
9.1. Study Design.....	18
9.2. Setting and Population.....	18
9.2.1. Setting.....	18
9.2.2. Inclusion Criteria	18
9.2.3. Population of Interest	18

CPRD	Clinical Practice Research Datalink
CRF	case report form
DA	Disease Analyzer
DPP-4 inh.	dipeptidyl peptidase-4 inhibitors
EHR	electronic health record
EMA	European Medicines Agency
ENCePP	European Network of Centres for Pharmacoepidemiology and Pharmacovigilance
ERB	Ethical review board
GFR	glomerular filtration rate
GLP-1 RAs	Glucagon-like peptide-1 receptor agonists
GVP	good pharmacovigilance practices
HbA1c	haemoglobin A1c (glycated haemoglobin)
HDL-C	high density lipoprotein cholesterol
ICD	International classification of disease
ICD-10	International classification of disease, 10 th version
ICH	International Conference of Harmonisation

ISAC	Independent Scientific Advisory Committee
ISPE	International Society for Pharmacoepidemiology
LDL-C	low density lipoprotein cholesterol
MAH	marketing authorisation holder
NPR	National Prescription Registry
PASS	post-authorization safety study
PBRER	periodic benefit-risk evaluation report
PSUR	periodic safety update report
RMP	risk minimization plan
SAE	serious adverse event
SAP	statistical analysis plan
SAR	serious adverse reaction
SIDIAP	Sistema de Información para el Desarrollo de la Investigación en Atención Primària (The Information System for the Development of Research in Primary Care)
SmPC	summary of products characteristics
SOP	standard operating procedure
SPDR	the Swedish prescribed drug register
STROBE	strengthening the reporting of observational studies in epidemiology
T2DM	type 2 diabetes mellitus
UK	United Kingdom

3. Responsible Parties

Project team:

Sponsor: Eli Lilly and Company

Sponsor's EU Qualified Person for Pharmacovigilance (QPPV):

[name], EU QPPV

Main Author: IMS Health, RWES/HEOR Department

[name] Medical director Pharmacoepidemiology Lead, North Europe and Africa

Co-Author: Eli Lilly and Company

[name], Pharmacoepidemiologist

4. Abstract

Title: Utilisation of dulaglutide in European countries: A cross-sectional, multi-country and multi-source drug utilisation study using electronic health record databases.

Version 1.0 Date: 01 May 2016

Rationale and background:

Glucagon-like peptide-1 receptor agonists (GLP-1 RAs) are incretin mimetics; they stimulate insulin secretion in a glucose-dependent manner (1,2), and are widely used as glucose-lowering drugs in the treatment of patients with type 2 diabetes mellitus (T2DM) (3).

Dulaglutide is a long-acting GLP-1 RA. Its structure protects it from inactivation by dipeptidyl peptidase-4 (DPP-4) and confers a half-life up to ~4.7 days in humans (4). As a result of this relatively long half-life, dulaglutide can be administered once weekly.

Dulaglutide was approved in the European Union (EU) for the treatment of T2DM in November 2014 (5).

To better understand the utilisation of dulaglutide in real world conditions in the EU, this drug utilisation study (DUS) aims to describe the use of dulaglutide with regard to off-label use and medication errors, as well as the use in subpopulations of patients for which little data exist, including patients with severe renal failure, heart failure, hepatic disease, or severe gastrointestinal disease; children, adolescents, and elderly with T2DM; and pregnant and breastfeeding women.

Research question and objectives:

The purpose of this study is to describe how dulaglutide is used among different patient groups in European countries.

Primary objective:

To describe the frequency of dulaglutide use in the population and characterise by age, gender, main co-morbidities and main co-prescriptions overall and within the following subgroups of interest:

- Populations of interest:
 - Patients with severe renal failure
 - Patients with hepatic disease
 - Patients with heart failure
 - Patients with severe gastrointestinal disease
 - Children and adolescents <18 years of age
 - Elderly patients ≥ 75 years
 - Pregnant and breastfeeding women
- Medication use:
 - Medication errors
 - Off-label use

Secondary objective:

- To describe the off-label use among each subgroup of the populations of interest.

Study design:

A multi-country, multi-source, cross-sectional, descriptive study using longitudinal data collected from European electronic health record (EHR) databases.

Several countries will be selected from the databases under consideration (France, Germany, Spain, Sweden, and the United-Kingdom [UK]). The justification of the selected countries will be based on the feasibility assessment results and will depend on the market uptake and volume of dulaglutide in each country.

The study will describe the utilisation of dulaglutide for at least three years following the launch of dulaglutide.

Population:Inclusion criteria:

- Patients for whom a treatment with dulaglutide is initiated during the observation period.
- Patients having at least 6 months of available continuous history prior to the date of the first dulaglutide prescription.

No exclusion criteria will be applied.

Subgroups of interest:

- Populations of interest:
 - Patients with severe renal failure
 - Patients with hepatic disease
 - Patients with heart failure
 - Patients with severe gastrointestinal disease
 - Children and adolescents <18 years of age
 - Elderly patients ≥ 75 years
 - Pregnant and breastfeeding women
- Medication use:
 - Medication errors
 - Off-label use

Variables:

The following variables will be extracted from databases, whenever available, which will be analysed at the baseline (6-month period prior to dulaglutide initiation) and/or index date (dulaglutide initiation):

- Patients' demographics (age and gender) at baseline
- Relevant comorbidities
- Medical history: disease diagnoses

- Concomitant anti-diabetes medications (ADMs) and other drug exposures
- Average daily dosage of prescriptions
- Prescriptions in combination with other ADMs

Data sources:

The following European EHR databases will be used for the feasibility. A subset of these databases will be then selected for the actual study:

- France: IMS Disease Analyzer (French DA)
- Germany: IMS Disease Analyzer (German DA)
- Spain: The Information System for the Development of Research in Primary Care (SIDIAP)
- Sweden: National Patient Register (NPR) and Swedish Prescribed Drug Register (SPDR)
- United Kingdom: Clinical Practice Research Datalink (CPRD)

Study size:

The first analysis and report will commence once at least 1000 patients initiated with dulaglutide become available in the EHR databases with at least 100 patients in the smallest country. All eligible patients of each selected database will be included in the study. Such a sample size would provide a precision of 3% for the entire sample and a minimum precision of 10% for the country with the smallest sample around an estimated proportion of 50% with 95% confidence intervals.

Data analysis:

The analysis will be performed per country, on the overall data set of eligible patients, 0.75 or 1.5 mg prescription of dulaglutide, and per subgroups.

Data coming from different databases/countries will not be pooled. The analysis will be done per year, and will not be cumulative. Thus data coming from different years will not be pooled either.

The statistical analysis will be descriptive including standard univariate analysis; no inferential statistical analyses will be conducted. Continuous variables will be described by the number of available values: mean, standard deviation, median, Q1, Q3, minimum and maximum. Data not available in the databases will be reported as missing. Categorical variables will be described as the total number of available values and relative percentage per subgroup of interest. Where relevant, 95% confidence intervals will be calculated for the endpoints.

The statistical analysis will be conducted using the SAS[®] software V9.2 or later on Windows[™] (SAS Institute, North Carolina, USA).

Milestones:

The start and end of data collection may change due to the market uptake of dulaglutide and data capture by the databases of respective countries. The dates below are estimates and may need to be updated following feasibility assessment.

Milestones	Planned date
Start of data collection	Estimated Q3 2016 The start of data collection may change due to the market uptake of dulaglutide in the countries and protocol approval from PRAC.
End of data collection	Estimated Q2 2019 The end of data collection may change due to the market uptake of dulaglutide in the countries.
Feasibility assessment report	Estimated Q3 2016
Interim report 1	Estimated Q4 2016
Interim report 2	Estimated Q4 2017
Interim report 3	Estimated Q4 2018
Registration in the EU PAS register [EU PASS Only]	Estimated Q1 2016
Final report of study results	Approximately 5 years from market authorisation (estimated Q4 2019)

5. Amendments and Updates

Not applicable.

6. Milestones

Milestone	Planned date
Start of data collection	Estimated Q3 2016 The start of data collection may change due to the market uptake of dulaglutide in the countries and protocol approval from PRAC.
End of data collection	Estimated Q2 2019 The end of data collection may change due to the market uptake of dulaglutide in the countries.
Feasibility assessment report	Estimated Q3 2016
Interim report 1	Estimated Q4 2016
Interim report 2	Estimated Q4 2017
Interim report 3	Estimated Q4 2018
Registration in the EU PAS register [EU PASS Only]	Estimated Q1 2016
Final report of study results	Approximately 5 years from market authorisation (estimated Q4 2019)

7. Rationale and Background

Glucagon-like peptide-1 receptor agonists (GLP -1 RAs) are incretin mimetics. Similar to endogenous hormone GLP-1 (1), they inhibit glucagon secretion, delay gastric emptying and suppress appetite. They stimulate insulin secretion in a glucose-dependent manner; insulin release stops when the plasma glucose level is low (3 mmol/l) (2). The GLP-1 RAs are widely used as glucose-lowering drugs in the treatment of T2DM (3).

Five GLP-1 RAs are currently approved worldwide for treatment of adults with T2DM: exenatide (2 forms with daily/weekly administration: Byetta® was approved by the EMA in November 2006 / Bydureon® in 2011, Astra Zeneca), liraglutide in July 2009 (Victoza®, Novo Nordisk), lixisenatide in February 2013 (Lyxumia®, Sanofi), albiglutide in March 2014 (Eperzan®, GlaxoSmithKline) and dulaglutide in November 2014 (Trulicity®, Eli Lilly and Company). Currently all are marketed in Europe. Additionally, one formulation which comprises insulin Degludec and liraglutide, IDegLira (Xultophy®, Novo Nordisk) as single-device combination therapy was approved in September 2014.

Dulaglutide is a long-acting GLP-1 RA. Its structure protects it from inactivation by dipeptidyl peptidase-4 (DPP-4) and confers a half-life up to ~4.7 days in humans (4). As a result of this relatively long half-life, dulaglutide can be administered once weekly which may offer an advantage compared to some competitors, such as short acting exenatide which is given twice daily, and liraglutide or lixisenatide which are used once daily. It is to be noticed that as dulaglutide, long-lasting exenatide (Bydureon®), and albiglutide (Eperzan®) are also used once weekly.

The European Union (EU) Commission approved the dulaglutide injectable solution for the treatment of T2DM in November 2014 (5).

As part of the risk management plan (RMP), Eli Lilly, the Marketing Authorisation Holder (MAH) of dulaglutide has agreed to conduct a DUS to describe the use of dulaglutide in particular subgroups of patients in several databases in European countries.

The rationale for this study is the need to gain knowledge about dulaglutide utilisation in real world conditions, as well as information on off-label use, medication errors, and the use in subpopulations of patients for which little data exist (i.e., patients with severe renal failure, heart failure, hepatic disease, or severe gastrointestinal disease; children and adolescents with T2DM < 18 years of age; elderly \geq 75 years; and pregnant and breastfeeding women).

8. Research Question and Objectives

The purpose of this study is to describe how dulaglutide is used among different patient groups in European countries.

Primary objective:

To describe the frequency of dulaglutide use in the population and characterise by age, gender, main co-morbidities and main co-prescriptions overall and within the following subgroups of interest:

- Populations of interest:
 - Patients with severe renal failure
 - Patients with hepatic disease
 - Patients with heart failure
 - Patients with severe gastrointestinal disease
 - Children and adolescents <18 years of age
 - Elderly patients ≥ 75 years
 - Pregnant and breastfeeding women
- Medication use:
 - Medication errors
 - Off-label use

Secondary objective:

To describe the off-label use among each subgroup of populations of interest.

9. Research Methods

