9.5. Study Size

9.5.1. Sampling

The real number of eligible patients included in the dulaglutide group will depend on the uptake and volume of the drug in each country.

The sample size formula, based on the normal approximation to the binomial distribution, for calculation of the number of subjects n required to determine a proportion p with a precision e with a two-sided α first-type error is the following:

$$n = \frac{p \times (1-p) \times z_{1-\alpha/2}^2}{e^2} \quad (1)$$

Based on this sample, and considering a confidence interval of 95%, in order to be able to determine any percentage with a precision of at least $\pm 5\%$, 384 subjects will be necessary. This corresponds to a hypothetical proportion of 50% which is generally considered acceptable as it yields to the largest sample size for each precision level. Respectively, a precision of at least $\pm 3\%$ or $\pm 10\%$ would necessitate a sample size of 1066 or 97 dulaglutide initiated patients.

In this study, assuming that we would like to be able to describe any proportion with a precision of at least 10% in each country, a minimum sample size of 100 cases is required for any of the countries. Assuming we want that the smallest country to represent at least 10% of the whole sample, it was pragmatically decided to start the study when data on 1,000 initiations of dulaglutide are available in the considered databases with at least 100 cases available in the smallest contributing country.

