9.7. Data Analysis

9.7.1. General Statistical Considerations

The analysis will be performed per country, on the overall data set of eligible patients and per subpopulations.

Data coming from different databases/countries will not be pooled due to the difference between structure of panels of health care professionals who contribute the data, asynchronicity of databases, heterogeneity in data structure, coding, and prescribing practices. The analysis will be done per year, and will not be cumulative. Thus data coming from different years will not be pooled either.

The statistical analysis will be descriptive including standard univariate analysis; no inferential statistical analyses will be conducted. Continuous variables will be described by the number of available values, mean, standard deviation, median, Q1, Q3, minimum and maximum. Data not available in the databases will be reported as missing. Categorical variables will be described as the total number of available values and relative percentage per subgroup of interest. When relevant, 95% confidence intervals will be calculated for the endpoints.

The statistical analysis will be conducted using the SAS[®] software V9.2 or later on Windows[™] (SAS Institute, North Carolina, USA).

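### The abstract's 3% precision for the entire sample belongs to no planned analysis, because countries and years are never pooled

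*Protocol*

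**What the plan says.** Under Study size, the abstract sets the start of analysis at 1000 dulaglutide initiators or more over all databases, with 100 or more in the smallest country. It attaches two worst-case precisions to that threshold: "Such a sample size would provide a precision of 3% for the entire sample", and 10% for the smallest country.

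Section 9.5.1 gives the formula behind these figures. It notes that ±3% or ±10% "would necessitate a sample size of 1066 or 97 dulaglutide initiated patients", and it justifies the minimum of 100 per country by the wish to "describe any proportion with a precision of at least 10% in each country".

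Section 9.7.1 has the analysis done country by country and year by year. On countries: "Data coming from different databases/countries will not be pooled due to the difference between structure of panels". On years: "Thus data coming from different years will not be pooled either". The abstract carries the same two rules directly after its study-size paragraph. Mock Table 9.7.4-1 is headed by a single country, so its column for all patients means all patients of that country.

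**The concern.** A precision statement should describe an estimate that will be reported. The 3% figure needs one proportion computed from all 1000 patients, and the analysis rules exclude that proportion. A reader of the abstract, including the regulator, would expect the main results to be known to about 3 points, when at the minimum country size they are known to about 10.

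A second question is how far the 10% reaches. The primary objective characterises patients within nine subgroups, and the secondary objective describes off-label use within each population of interest. Those percentages have the subgroup as denominator, and the study-size section gives no precision for them.

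**Working it through.** **Inputs from the protocol.** The confidence level ("considering a confidence interval of 95"%), the two-sided error ("with a two-sided α first-type error") and the worst-case proportion ("This corresponds to a hypothetical proportion of 50"%) are in Section 9.5.1. The threshold of 1000, with at least 100 in the smallest country, is in the abstract and Section 9.5.1. The number of countries, three, is in Section 9.5.2.

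**Formulas.** n = p(1−p)z²/e², and half-width e = z√(p(1−p)/n). With z = 1.96 and p = 0.5 these become n = 0.9604/e² and e = 0.98/√n.

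**Reproducing the plan's figures.**
- ±5%: 0.9604/0.0025 = 384.2 (stated 384).
- ±3%: 0.9604/0.0009 = 1067.1 (stated 1066).
- ±10%: 0.9604/0.01 = 96.04, rounded up to 97 (stated 97).
- n = 1000: 0.98/√1000 = 3.10%.
- n = 100: 0.98/√100 = 9.80%.

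The stated figures reproduce to within rounding.

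**Precision at the level analysed.** Take exactly 1000 initiators, all in one annual wave, split over three countries with at least 100 in each. The largest possible country then has 1000 − 100 − 100 = 800.

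| Country size | Half-width at p = 50% |
|---|---|
| 100 (minimum) | 0.98/√100 = 9.8% |
| 333 (three equal countries) | 0.98/√333 = 5.4% |
| 800 (largest possible) | 0.98/√800 = 3.5% |

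No country reaches 3% at the threshold. That takes about 1,067 initiators in one country and one year.

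**Within subgroups.** The protocol gives no subgroup shares, so the shares here are assumptions.
- Country of 100, share 30%: n = 30, 0.98/√30 = 17.9%.
- Country of 100, share 10%: n = 10, 0.98/√10 = 31.0%.
- Country of 333, share 30%: n ≈ 100, 9.8%.
- Country of 800, share 20%: n = 160, 0.98/√160 = 7.7%.

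By the plan's own figure of 97 for ±10%, a subgroup with a 30% share needs a country of 97/0.30 ≈ 324, and one with a 10% share needs 97/0.10 = 970. All these are worst cases: proportions far from 50% have narrower intervals, and at n = 10 the normal approximation is only a rough guide.

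**Effect of cumulating years in one country.** Assume 100 initiators in each of three years. The half-width goes from 9.8% to 0.98/√300 = 5.7%. The exact upper 95% limit when no case is seen goes from 1 − 0.025^(1/100) = 3.6% to 1 − 0.025^(1/300) = 1.2%.

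**The case against.** The best defence is that the 3% for the whole sample stands in one abstract sentence. Section 9.5.1 rests the start rule on the 10% per country and on the smallest country making up a tenth of the sample. The study is descriptive, tests no hypothesis, and no decision hangs on the 3%. This is right about the consequences and keeps the point modest, but the sentence still states a precision that no planned result will have.

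Several stronger readings are tempting, and the protocol does not support them.

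- **That the 10% fails in every subgroup.** The 10% is stated per country, and 100 patients deliver 9.8%. The 100 is a floor with no cap, since all eligible patients are included, and a common subgroup in a larger country can meet 10%. How often children, pregnant women or off-label users occur among all initiators also uses the country denominator and keeps the 10%. What is missing is a statement about percentages within subgroups; no promise about them is broken.
- **That the sample-size arithmetic is wrong.** 1066 against 1067, and 3.1% against 3%, are rounding, and Section 9.5.1 openly calls the choice of 1000 pragmatic.
- **That refusing to pool years is an error.** The reasons in Section 9.7.1 concern databases and countries, and no separate reason is given for years. Even so, annual tables fit the three calendar-year waves of Section 9.1 and a newly launched drug, so this is a design choice.
- **That the interval method for rare proportions is missing.** Section 9.7.5 leaves statistical methodology to the SAP.

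**Conclusion.** The 3% claim is wrong as written. It is correct arithmetic for a pooled estimate that the same abstract and Section 9.7.1 exclude. At the threshold, the worst-case half-width of what will be reported lies between 3.5% and 9.8% per country, with 5.4% if the three countries are equal. This range assumes three countries, exactly 1000 initiators and one annual wave. A country with more initiators would do better, and about 1,067 in one year would give 3% for that country, though that would still not be precision for the entire sample.

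The 10% per country stands for proportions of all initiators. At the minimum country size it does not extend to percentages within small subgroups, where the half-width would be about 18% to 31% for assumed shares of 30% to 10%. The protocol should say so, because its objectives ask for those percentages.

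**What to change.** 1. In the abstract, delete the 3% claim and state precision per country and year: 9.8% at the minimum of 100 initiators, at p = 50%.
2. In Section 9.5.1, say that the 10% applies to proportions of all initiators in a country. Add that percentages within subgroups are less precise, with illustrative values labelled as resting on assumed subgroup sizes.
3. Optionally, keep the annual tables and add to the final report one cumulative table per country for the rare subgroups. Section 9.3 defines initiation by the absence of an earlier dulaglutide record, so the yearly sets within a database should hardly overlap. This is an improvement and not the correction of an error, and it would need a matching exception to the no-pooling rule for years.

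The first two changes are wording only and leave data collection as it is. Their cost is a less favourable stated precision. The third adds one set of tables per country and averages over any change in prescribing between years, which the annual tables would still show.
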